10.2 Secondary study parameter(s)

Statistical comparison of quality of life, body image, cosmetic results and abdominal wall function between patient groups (small vs large bites technique and with or without incisional hernia) will be done by multilevel analysis (linear mixed-effects model with random effect for each patient) (7).

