2. OBJECTIVES

Primary Objective:

The primary objective of the original STITCH trial was reduction of the incidence of an incisional hernia after open, elective abdominal surgery. The primary objective of the present study is to determine the difference in incidence of incisional hernia between the intervention group and the control group of the original STITCH trial after 10 years of follow-up from the time of randomization,.

Secondary Objectives:

The secondary objectives of this follow-up study are to measure quality of life (QoL), body image and cosmetic results and abdominal wall function in those patients who are still alive.

[figure not shown]
In addition, all information is collected regarding the abdominal wall hernia (presence, location, duration, size, recurrence, repair) and other abdominal wall related complications such as: open abdomen, enterocutaneous fistula, wound problems, burst abdomen, number of abdominal reoperations, number of hospital admissions (and total days) with/without development of ileus.

STUDY DESIGN

The original STITCH trial (NCT01132209) was a multicenter double-blind prospective randomized controlled trial who randomly assigned 560 patients between October 2009 and March 2012 in the intervention group (small bites) or in the control group (large bites). Ultimately, 268 patients were included in the intervention group and 277 patients in the control group. A total of 545 patients.

This current study is a long-term (10-13 years) follow-up of the original STITCH trial.

The flowchart below graphically depicts the process of approaching the patients who were included in the original STITCH trial. On the original informed consent form of the STITCH trial patients were asked if they agreed to being contacted for a follow-up study after completion the original trial.

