8.1.2 Secondary study parameters/endpoints

The secondary outcomes will be measured using five validating questionnaires. Quality of Life (QoL), body image, cosmetic results and abdominal wall function (AWF) will be reported from all patients who are still alive with consent for participation. Three of the five questionnaires have also been validated in a Dutch version. The other two were translated from English. The following measuring instruments will be used for this:

- Quality of Life
 - MOS SF-36: This questionnaire consists of 36 items. The item scores are summed to scale scores and transformed to a 100-point scale. A higher score indicates better health status(9).
 - EQ-5D; This questionnaire consists of a total of fourteen items. The answers can be converted to a total score representing the health profile(10).
- Body image: Dresden Body Image Questionnaire (DBIQ); consists of 35 items and five subscales (11).
- Cosmetic results: Body Image Questionnaire (BIQ); the questionnaire consists of ten items evaluating body image, cosmesis and self-confidence before and after surgery. The higher the score in the first five items, the lower the body image. The lower the score in items 6, 7 and 8, the lower cosmesis assessment. The last two items are about self-confidence before and after surgery where 1 is "not very confident" and 10 is "very confident." (12).
- AWF: Hernia-Related Quality of Life Survey (HerQLes); this questionnaire consists of twelve statements where the patient can choose from six options, how much they agree or disagree with the statement. The higher the score, the greater the burden of the abdominal wall(13).

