8.1.3 Other study parameters

Demographic characteristics collected during randomization during the original trial are used for follow-up. This includes gender, age, length and weight (BMI), smoking history (yes or no), medical history and ASA class.

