10.3 Other study parameters

Demographics and baseline characteristics will be reported using descriptive statistics.

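### Protocol 10.2 gives the non-randomised hernia v no-hernia comparison the same model as the randomised comparison, names no adjustment for it, and leaves hernia status undefined

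*Protocol*

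**What the plan says.** Protocol 10.2 sets one method for two groupings. The patient-reported outcomes are to be compared "between patient groups (small vs large bites technique and with or without incisional hernia) will be done by multilevel analysis", and the model is described as a "linear mixed-effects model with random effect for each patient". No other model term is given.

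The baseline variables appear in two places. Protocol 8.1.3 says "Demographic characteristics collected during randomization during the original trial are used for follow-up" and lists them: "This includes gender, age, length and weight (BMI), smoking history (yes or no), medical history and ASA class". Protocol 10.3 states the only analysis for them: "Demographics and baseline characteristics will be reported using descriptive statistics".

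On purpose, Protocol section 2 says "The secondary objectives of this follow-up study are to measure quality of life (QoL), body image and cosmetic results and abdominal wall function", among patients still living. Protocol 8.1.2 limits the data in the same way: the outcomes "will be reported from all patients who are still alive with consent for participation".

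On hernia detail, Protocol section 2 says "all information is collected regarding the abdominal wall hernia (presence, location, duration, size, recurrence, repair", along with other wall complications. Protocol 10.2 does not say which of these facts places a patient in the hernia group.

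**The concern.** Only the closure technique was randomised. Comparing scores by technique draws on that randomisation, subject to who survives and consents. Comparing scores by hernia status does not: a hernia develops afterwards, and patients who develop one may differ in BMI, age, sex, smoking and ASA class. Each of these can plausibly affect quality-of-life and body-image scores in its own right. A single model for both contrasts treats them as having equal standing.

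The Introduction says that a hernia can strongly affect body image and quality of life. A tested difference between patients with and without one will be read in that light unless the protocol says how far the reading may go. Part of the difference could instead reflect body weight and comorbidity.

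The grouping itself is a second problem. The primary outcome is a 10-year rate, so a hernia repaired years ago still counts as an event. The questionnaires are completed once, 10 to 13 years after randomisation. Without a definition, the reader cannot tell whose scores are being compared.

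**Working it through.** **No figure to reproduce.** The protocol gives no sample size, alpha, SD or effect size for this analysis. Protocol 4.4 gives only the 545 patients who completed one year.

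**Step 1: what the described model can remove.** The terms described in 10.2 are group and a random effect per patient. The random effect represents variation between patients that is taken to be unrelated to group. If BMI differs between hernia groups and affects the score, that part of the variation is related to group and stays in the group coefficient. Only a covariate term, or an equivalent design step, takes it out. 10.2 names none, and 10.3 assigns the baseline variables to description.

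**Step 2: scale of the groups.** From the Introduction and the study design text, hernias at one year are about 0.21 × 277 = 58 (large bites) and 0.13 × 268 = 35 (small bites). That is 93 of 545, or 17%. The share at 10 years among responders is not given.

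**Step 3: possible size, illustration only.** All inputs here are assumed.

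- Bias in SD units = (difference in the covariate between hernia groups, in SD) × (SD change in score per SD of covariate).
- Difference 0.1 to 0.5 SD; slope 0.1 to 0.3.
- Smallest: 0.1 × 0.1 = 0.01 SD. Largest: 0.5 × 0.3 = 0.15 SD, for one covariate.
- With an assumed SD of 25 on a 100-point scale: 0.01 × 25 = 0.25 points to 0.15 × 25 = 3.75 points.

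Chance of declaring a difference when hernia itself has no effect, at an assumed two-sided alpha of 0.05, with n responders and hernia share h:

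- SE = √[1/(nh) + 1/(n(1 − h))]
- Rejection = 1 − Φ(1.96 − bias/SE) + Φ(−1.96 − bias/SE)

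| n | h | bias 0.03 SD | 0.06 SD | 0.09 SD | 0.15 SD |
|---|---|---|---|---|---|
| 150 | 17% | 5.2% | 5.9% | 7.0% | 10.6% |
| 150 | 35% | 5.4% | 6.4% | 8.2% | 14.2% |
| 250 | 17% | 5.4% | 6.5% | 8.3% | 14.5% |
| 250 | 35% | 5.6% | 7.4% | 10.4% | 20.5% |
| 350 | 17% | 5.5% | 7.1% | 9.7% | 18.4% |
| 350 | 35% | 5.8% | 8.3% | 12.7% | 26.8% |

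The effect runs from negligible to material depending on inputs that the protocol does not supply. Biases from several covariates cannot simply be summed: they may differ in sign, and the covariates are correlated.

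**Step 4: the yes/no split under each reading.**

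| Patient's state at the visit | Group if hernia means ever | Group if hernia means at the visit |
|---|---|---|
| Never had a hernia | without | without |
| Repaired, not present | with | without |
| Present | with | with |

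Under either reading, one group holds two different states. The single visit with examination and ultrasound (Protocol 8.3), with the recorded presence, recurrence and repair (section 2), is enough to separate all three.

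**The case against.** The strongest reply has three parts.

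**Silence is not a specification.** A reader might infer that 10.2 prescribes an unadjusted model. It does not: it names no covariates and excludes none. Protocol 8.1.3 says the baseline characteristics are used for follow-up without saying how, and describing them under 10.3 does not forbid modelling them. A covariate list is ordinary content for a statistical analysis plan, which may exist and is not shown. This stands as a limit on the wording. It does not remove the point, because the protocol text itself assigns one model to two contrasts of different standing and gives the baseline variables no role beyond description.

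**No causal claim is made.** A reader might infer that the hernia difference is meant as the effect or burden of hernia. The stated objective is to measure these outcomes, and a plain descriptive difference between the groups is legitimate for that purpose. This also stands. It is a reason to label the comparison, since 10.2 calls for a statistical comparison beside the randomised one with nothing to tell them apart.

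**Pooling of repaired and present hernias is one reading.** A reader might infer that 10.2 puts both in one group. That follows only if status means ever; if it means at the visit, repaired patients join those who never had a hernia. The objection is right, but neither reading gives a clean split.

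It is also true that the illustrated bias rests wholly on assumed inputs and is trivial at its lower end. The direction of the net error is not established either.

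**Conclusion.** The point holds in limited form. Protocol 10.2 does not separate the non-randomised hernia comparison from the randomised one and names no adjustment for it. If it is run as written, with baseline variables only described, the hernia difference in quality of life, body image and abdominal wall function is open to confounding. That BMI, age, sex, smoking and ASA class act as confounders is plausible, but the document has no data to show it. The size cannot be fixed: 0.01 to 0.15 SD per covariate is an assumed range, with a false-positive rate of about 5% at 0.03 SD and about 11% to 27% at 0.15 SD for 150 to 350 responders and 17% to 35% with a hernia.

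Separately, and without any assumed input, hernia status is undefined and either natural yes/no reading mixes clinical states.

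This concerns secondary outcomes only. The primary hernia-rate comparison does not depend on it.

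**What to change.** In Protocol 10.2, or in the analysis plan with a reference from 10.2, before the data are analysed:

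1. State the two contrasts separately: small v large bites as the randomised comparison, and hernia status as a non-randomised one.
2. For hernia status, add randomised arm and baseline age, sex, BMI, smoking and ASA class as fixed effects.
3. Classify status at the study visit as never / repaired and not present / present.
4. State that the hernia result is reported as an association.

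If the sponsor wants only an unadjusted description of the two groups, 10.2 should say so; items 1, 3 and 4 still apply.

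Covariates in the arm comparison are optional. They may improve precision but correct no error.

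The cost is mainly wording, as all the variables are already collected. The model spends five degrees of freedom on arm, age, sex, BMI and smoking, at least one on ASA class, and one more for the third hernia level. The hernia subgroups also become smaller: on the assumed ranges above, between about 26 (150 × 0.17) and 123 (350 × 0.35) patients with a hernia would be divided between repaired and present, so those estimates will be less precise.

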10.3 Other study parameters

Demographics and baseline characteristics will be reported using descriptive statistics.

10.4 Interim analysis (if applicable)

Not applicable, since no interim analysis is performed.

11. ETHICAL CONSIDERATIONS

11.1 Regulation statement

This study will be conducted in accordance with the principles of the Declaration of Helsinki (64th World Medical Association General Assembly, Fortaleza, Brazil, October 2013) This study has been exempted by the medical research ethics committee (MREC); in Dutch: Medisch Ethische Toetsings Commissie (METC). Following review of the protocol, the MREC concluded that this study is not subject to the Medical Research Involving Human Subjects Act (WMO). They concluded that the study is a medical/scientific research, but no patients are subjected to procedures or are required to follow rules of behavior.

11.2 Recruitment and consent

Patients who were included in the original STITCH trial and who are still alive will be approached by the study coordinator or the surgeon from the hospital they were included at the time, for participation in the follow-up study. Patients will only be approached if they have not checked the box on the Informed Consent Form of the original STITCH trial that they do not wish to be approached in the future for follow-up studies. Patients who indicated they had no objection to being approached will be contacted by telephone for participation and explanation of the study. If the patient approves, we will then send a subject information sheet with an informed consent form that allows the patient to make a well-informed and well-considered decision whether or not to participate in this follow-up study. The informed consent form can be returned free of charge by the patient when participation.

11.3 Objection by minors or incapacitated subjects

Not applicable as no minors or incapacitated subjects are included in this study.

11.4 Benefits and risks assessment, group relatedness

Undergoing an ultrasound, physical examination and completing several questionnaires may be considered burdensome for the patient.

11.5 Compensation for injury

As the study is not subject to the Medical Research Involving Human Subjects Act (WMO), the statutory obligation to provide insurance for subjects participating in medical research (article 7 of the WMO) also does not apply'.

11.6 Incentives

Patients will not receive any special incentives or additional treatment through participating in the study. Travel costs can be reimbursed.

12. ADMINISTRATIVE ASPECTS, MONITORING AND PUBLICATION

12.1 Handling and storage of data and documents

Research data will be stored in a Castor database and will be handled confidentially. Data will be coded with e.g. A01, A02, B01, etc (the letter depends on the site of the inclusion). Research data that can be traced to individual persons can only be viewed by authorized personnel. These persons are members of the research team, members of the health care inspection, and members of the Medical Research Ethics Committee. Data review may be necessary in order to ensure the reliability and quality of the research. The handling of personal data should comply with the EU General Data Protection Regulation and the Dutch Act on Implementation of the General Data Protection Regulation. (in Dutch: Uitvoeringswet AVG, UAVG). Data will be stored at least 15 years after date of publication.

12.2 Monitoring and Quality Assurance

The principal investigator, a project leader, or an independent person will monitor quality of the data in the database by checking correctness and completeness of data for a random selection of 10% of patients, with a minimum of 10 patients per participating hospital. Data regarding disease, disease severity, treatment, and outcome will be checked.

12.3 Amendments

Amendments are changes made to the research after a favourable opinion by the accredited METC has been given. All amendments will be notified to the METC that gave a favourable opinion.

12.4 Annual progress report

Not applicable, as this study will not be subject to the Medical Research Involving Human Subjects Act (WMO).

12.5 Temporary halt and (prematurely) end of study report

The investigator will notify the accredited METC of the end of the study within a period of 8 weeks. The end of the study is defined as the last patient's last visit.

The sponsor will notify the METC immediately of a temporary halt of the study, including the reason of such an action.

In case the study is ended prematurely, the sponsor will notify the accredited METC within 15 days, including the reasons for the premature termination. Within one year after the end of the study, the investigator/sponsor will submit a final study report with the results of the study, including any publications/abstracts of the study, to the accredited METC.

12.6 Public disclosure and publication policy

The publication policy of CCMO will be maintained. This statement contains the basic principles on CCMO's position on the disclosure/ publication of research results obtained from subjects involving

human subjects. It is the opinion of CCMO that the results of scientific research involving human subjects must be disclosed unreservedly.

Authors of potential publications following the present study will be determined by measure of contribution to the study protocol, study execution and manuscript synthesis, where the final decision of authorship is made by the Principal Investigator.

For publication of this follow-up study, the STROBE guideline will be followed (14).

13. STRUCTURED RISK ANALYSIS

13.1 Potential issues of concern

Not applicable, as this study does not involve an investigational or non-investigational product.

a. Level of knowledge about mechanism of action

Not applicable

b. Previous exposure of human beings with the test product(s) and/or products with a similar biological mechanism

Not applicable

c. Can the primary or secondary mechanism be induced in animals and/or in ex-vivo human cell material?

Not applicable

d. Selectivity of the mechanism to target tissue in animals and/or human beings

Not applicable

e. Analysis of potential effect

Not applicable

f. Pharmacokinetic considerations

Not applicable

g. Study population

Not applicable

h. Interaction with other products

Not applicable

i. Predictability of effect

Not applicable

j. Can effects be managed?

Not applicable

13.2 Synthesis

Not applicable, as this study does not involve an investigational or non-investigational product.

